2. DESIGN AND METHOD

2.1 Study Site:

Study will be conducted University of Peradeniya.

2.2 Study Population:

Undergraduates who are currently having upper back pain for more than seven days will be selected as sample. Participants who will have sub-acute and chronic pain which means who will have pain more than a week or seven days will be selected as sample and who have subjected to any recent surgeries, recent fractures, accidents or injuries in upper back will be excluded from the study.

2.3 Study Setting:

Study will be conducted in Service unit of Department of physiotherapy at University of Peradeniya.

2.4 Study Design:

This study is a Randomized Control Trial, Double- Blinded study. Participants and assessors will be blinded. Participants will be allocated randomly in to two groups which are experimental group which will receive thoracic mobility exercises and control group which will receive myofascial release and joint mobilization treatment.

2.5 Hypothesis:

1. Hypothesis about difference in baseline characteristics of participants between control and experimental groups

Null Hypothesis: $H_0: \mu_1 - \mu_2 = 0$

There is no difference in baseline characteristics of participants between experimental and control group.

Alternate Hypothesis: $H_1: \mu_1 - \mu_2 \neq 0$

There is a difference in baseline characteristics of participants between experimental and control group

2. Hypothesis about differences in pain intensity between control group and experimental group.

Null Hypothesis: $H_0: \mu_1 - \mu_2 = 0$

There is no difference in pain intensity of participants between experimental and control group.

Alternate Hypothesis: $H_1: \mu_1 - \mu_2 \neq 0$

There is a difference in pain intensity of participants between experimental and control group

3. Hypothesis about differences in thoracic mobility (Range of Motion) between control group and experimental group.

Null Hypothesis: $H_0: \mu_1 - \mu_2 = 0$

There is no difference in thoracic mobility of participants between experimental and control group.

Alternate Hypothesis: $H_1: \mu_1 - \mu_2 \neq 0$

There is a difference in thoracic mobility of participants between experimental and control group

4. Hypothesis about differences in muscle strength of spinal extensors between control group and experimental group.

Null Hypothesis: $H_0: \mu_1 - \mu_2 = 0$

There is no difference muscle strength of spinal extensors of participants between experimental and control group.

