Alternate Hypothesis: $H_1: \mu_1 - \mu_2 \neq 0$

There is a difference in muscle strength of spinal extensors of participants between experimental and control group

5. Hypothesis about differences in disability of participants between control group and experimental group.

Null Hypothesis: $H_0: \mu_1 - \mu_2 = 0$

There is no difference in disability of participants between experimental and control group.

Alternate Hypothesis: $H1: \mu_1 - \mu_2 \neq 0$

There is a difference in disability of participants between experimental and control group.

2.6 Sample Size:

Sample size is Calculated by using G*power 3.1.9.4 software by assigning power 80% effective size 0.5, type I error = 0.05 and type II error = 0.2. Therefore calculated sample size was 42. Drop down rate of participants is assigned as 25 %. Therefore final sample size which obtained is 60 (Kang, 2021).

2.7 Sampling method:

Simple Random Sampling will be used as sampling technique as well as 30 Participants will be randomly allocated to each group. Participant will be allocated to the groups by using lottery method.

2.8 Data collection:

Undergraduates who are having upper back pain more than 7 days will be selected as sample and those who are having any contraindications, recent surgeries, fractures, accidents will be excluded from the students. Informed consent will be obtained from the participants. Participants will be allocated to one group by blindly select the number by lottery method. Thirty participants will be allocated randomly to each group. Allocation was concealed. Assessors will not be aware of intervention or control group and collect the demographic data, Pain assessment, Range of Motion and muscle strength at the baseline and after two weeks of intervention.

2.9 Data collection tool:

Measurement tool contains two sections such as pre-test and post-test questionnaire. In Pre-test questionnaire, there are six sections which includes personal details of the participants, pain related questions, Measurement of range of motion at base line, muscle strength at base line and pain-self-efficacy Questionnaire (PSEQ) at base line. In Post-test questionnaire, there are 4 sections which include, pain related questions

mainly pain intensity after two weeks, muscle strength after two weeks, Range of motion after two weeks and pain-self-efficacy Questionnaire (PSEQ).

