Personal details of the participants will be collected separately for the concealed allocation and participants will be identified by code number. Participants' age, gender, height, weight, BMI, family size, bread winner of the family, monthly income and financial support for the study will be collected in the demographic data section. In third section, questions related to occurrence of pain, pain duration and treatments which were undertaken for the pain will be collected from the participants.

VAS scale will be used to measure the intensity of pain in different situations which include present pain intensity, in sitting, in forward bending, in standing, in walking, in sleeping, in transferring and during day to day activities. Visual Analogue Scale will be used to measure the pain intensity. Subjects will be asked to mark the number between 0 and 10 that fits best to their pain intensity. Zero indicates 'no pain at all' whereas 10 represents 'the worst pain ever possible' (Figure 1). Measurement will be obtained in the baseline and at the end of two weeks.

[figure not shown]

Figure 1- VAS Scale

Thoraco-Lumbar flexion and Extension of thoracic spine Range of Motion will be taken in the fourth section. Measurement will be taken by using measuring tape. Measurement will be taken at the baseline and after two weeks. In the fourth section, muscle strength of thoracic spine extensors will be measured using Oxford-Grading Scale. Measurement will be taken at the baseline and after two weeks. The Oxford Muscle Scale is a numerical rating scale used to quantify the power or strength produced by the contraction of a muscle. The scale was originally developed by a UK government research group called the Medical Research Council (MRC). Reliability of the scale

explained by Intraclass Correlation Coefficient (ICC) and Interrator Reliability. It shows high ICC coefficient of 0.95 (ranging from 0.92 to 0.97) (Hermans et al., 2012).

Muscle Strength Grading Scale (Oxford Scale)	
0/5	No Contraction
1/5	Visible/palpable muscle contraction but no movement
2/5	Movement with gravity eliminated
3/5	Movement against gravity only
4/5	Movement against gravity with some resistance
5/5	Movement against gravity with full resistance

Table 1

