In the sixth section, The Pain Self-Efficacy Questionnaire (PSEQ) is a 10-item questionnaire developed to assess the confidence people with ongoing pain have in performing activities while in pain. The PSEQ has high internal consistency (0.92 Cronbach's alpha) and test-retest reliability is high of a 3-month period.

	0 "not at all confident"	1	2	3	4	5	6 "completely confident"
1. I can enjoy things, despite the pain.							
2. I can do most of the household chores (e.g. tidying-up, washing dishes, etc.), despite the pain.							
3. I can socialise with my friends or family members as often as I used to do, despite the pain.							

4. I can cope with my pain in most situations.						
5. I can do some form of work, despite the pain. ('work' includes housework, paid and unpaid work).						
6. I can still do many of the things I enjoy doing, such as hobbies or leisure activity, despite pain.						
7. I can cope with my pain without medication.						
8. I can still accomplish most of my goals in life, despite the pain.						
9. I can live a normal lifestyle, despite the pain.						
10. I can gradually become more active, despite the pain.						

Table 2

2.10 Ethical Considerations:

Ethical approval will be obtained from the Institutional Review Board of Bangladesh Health Professional Institute. Written informed consent will be obtained from all the subjects who are willing to participate in the study. Participation in this research is entirely voluntary basis and the participants have the right to withdraw from the study at any time.

2.11 Outcome measures:

Baseline outcome measures are demographic characteristics of participants such as age, gender, BMI, family size, bread winner of the family, monthly income and financial

support for study; Pain duration; Pain intensity at present moment, sitting, forward bending, standing, walking, sleeping, transferring and pain when performing day to day activities; Range of Motion of thoraco-lumbar flexion and extension; Muscle strength of thoracic spine extensors and overall scale of Pain-Self- efficacy Questionnaire. After two weeks same outcome measures will be obtained other than demographic characteristics and pain duration.

2.12 Data analysis:

Two sample t test will be used to compare the group at baseline to determine the sample characteristics in the both group will be statistically equal. To find out the significant variation in the group after the intervention again two sample t test will be used.

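### The groups are compared after treatment without adjustment for baseline values already collected, which costs precision, and the baseline t test does not guard against chance imbalance

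*Combined protocol and SAP*

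**What the plan says.** Section 2.12 (Data analysis) has two sentences. The first uses a two-sample t test to "compare the group at baseline to determine the sample characteristics in the both group will be statistically equal". The second covers the treatment effect: "To find out the significant variation in the group after the intervention again two sample t test will be used". Neither the protocol nor its annexes name ANCOVA, a covariate, a change score or a mixed model, and nothing says what follows if a baseline test is significant.

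Section 2.11 (Outcome measures) adds: "After two weeks same outcome measures will be obtained other than demographic characteristics and pain duration". Twelve efficacy measures therefore exist at both times: eight pain VAS items, two range-of-motion measures, extensor strength on the Oxford grade, and the PSEQ total. Section 2.9 confirms the timing for the VAS ("Measurement will be obtained in the baseline and at the end of two weeks"), and the pre-test and post-test questionnaires in Annex II carry the same items.

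Hypothesis 1 in section 2.5 makes baseline equality a formal null: "There is no difference in baseline characteristics of participants between experimental and control group". The alternatives are two-sided, for example "There is a difference in pain intensity of participants between experimental and control group". Section 2.6 uses an effect size of 0.5 of unnamed type, 80% power and 5% type I error, and arrives at 42 participants, raised to 60 for an assumed loss of 25%. Section 2.7 allocates 30 per group by lottery and describes no stratification.

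**The concern.** When an outcome is measured before and after treatment, part of the follow-up variation is only where each participant started. A plain t test on follow-up values leaves that variation in the error term. The interval is wider and the power lower than the same data allow.

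There is also a conditional problem. Over all possible randomisations the unadjusted difference is unbiased, but only one randomisation is run. If one group happens to start with more pain, part of that gap carries into the two-week difference, in proportion to the baseline-to-follow-up correlation.

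The plan appears to rely on the baseline t test here, treating a non-significant result as showing that the groups are equal. Such a test neither corrects the estimate nor rules out a sizeable gap in a trial of 60. Under proper randomisation, any baseline difference is due to chance, so Hypothesis 1 tests something already known.

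**Working it through.** **Inputs.** From the documents: effect size 0.5, 5% type I error, 80% power, 42 raised to 60, 25% loss (section 2.6); 30 per group (section 2.7); two-sided alternatives (section 2.5). Assumed: 0.5 is Cohen's d; the baseline-to-follow-up correlation r is 0.3, 0.5 or 0.7 (the documents give none); SD is equal at both times. Completers after the planned loss: 60 × 0.75 = 45.

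**The plan's own figure.** The stated 42 is not reproduced. A two-sided two-sample t test with d = 0.5 and 80% power needs 64 per arm, 128 in total. Nor does 25% loss turn 42 into 60: 42/0.75 = 56. These are separate matters. The present point does not depend on them.

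**Formulas.** All use the noncentral t distribution, with n per arm and N in total.
- Two-week t test: noncentrality d/√(2/n), N − 2 degrees of freedom.
- ANCOVA: residual SD multiplied by √(1 − r²), so d becomes d/√(1 − r²), with N − 3 degrees of freedom.
- Change-score t test: d becomes d/√(2(1 − r)), with N − 2 degrees of freedom.
- 95% interval half-width: critical t × √(2/n), multiplied by √(1 − r²) for ANCOVA.

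**Example, N = 45, r = 0.5.** √(2/22.5) = 0.298. Unadjusted: 0.5/0.298 = 1.68, power 37%, half-width 2.017 × 0.298 = 0.60 SD. ANCOVA: 1.68/√0.75 = 1.94, power 47%, half-width 2.018 × 0.298 × 0.866 = 0.52 SD.

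| | Two-week t test | ANCOVA, r = 0.3 / 0.5 / 0.7 | Change-score t test, r = 0.3 / 0.5 / 0.7 |
|---|---|---|---|
| Power, N = 45 | 37% | 40 / 47 / 63% | 28 / 37 / 56% |
| Power, N = 60 | 48% | 51 / 59 / 76% | 36 / 48 / 69% |
| Half-width, N = 45 | 0.60 SD | 0.57 / 0.52 / 0.43 SD | – |
| Half-width, N = 60 | 0.52 SD | 0.49 / 0.45 / 0.37 SD | – |

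ANCOVA would need r = 0.81 with 45 completers, or 0.73 with 60, to reach 80% power.

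**Validity.** In simulation (40,000 trials per setting) both the two-week t test and ANCOVA were unbiased, with type I error between 4.8% and 5.1%.

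**Chance imbalance, 30 per arm as randomised.** The standard error of a baseline gap is √(2/30) = 0.258 SD.
- Largest non-significant gap: 2.002 × 0.258 = 0.52 SD, about the size of the whole planned effect.
- Median absolute gap: 0.674 × 0.258 = 0.17 SD.
- Probability of a gap above 0.25 SD: 2 × P(Z > 0.25/0.258) = 33% for a given outcome.
- Expected shift in the unadjusted difference, r × gap: for a gap of 0.25 SD, 0.08/0.13/0.18 SD.

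Among 45 completers (standard error 0.298 SD) the same quantities are 0.60 SD, 0.20 SD and 40%.

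**Does a non-significant baseline test protect?** In simulation (20,000 trials per setting, 21 and 30 per arm), take trials where the baseline test was non-significant but its |t| exceeded 1. The type I error of the two-week t test was then about 6%, 7 to 7.5% and 8.5% at r = 0.3/0.5/0.7, while ANCOVA stayed near 5%. Over all trials with a non-significant baseline test the t test was somewhat conservative (3.3% to 4.8%), so the excess lies in the larger gaps that still pass as equal.

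**The case against.** The strongest reply is that an unadjusted t test in a randomised trial is a legitimate analysis. That stands: this is a point about efficiency and conditional bias, not an invalid test.

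Section 2.12 also does not literally specify two-week values. Its wording might mean change, and section 3 speaks of improvement. If change were tested, the baseline would not be ignored. This reading cannot be excluded, but no change score is mentioned anywhere, and it would not rescue the plan. A change-score test has less power than ANCOVA at each correlation shown, and less than the two-week t test when r is below 0.5.

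The size of the gain rests on an assumed correlation, and 12 different outcomes need not share one. At r = 0.3 the gain is 3 to 4 points of power, too little to alter a decision. That stands too, as does the fact that adjustment does not repair the sample size.

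The plan attaches no consequence to the baseline test, so that test does not itself distort the treatment estimate. True, but then it offers no protection either. Finally, the ordinal model suggested below for the Oxford grade is a side point, and its stability with about 22 per arm has not been checked. The main recommendation does not need it.

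**Conclusion.** The concern holds. The planned test is valid, but it makes no stated use of baseline values that are collected for every efficacy outcome. With d = 0.5, two-sided 5% error and 45 completers, adjustment raises power from 37% to 40/47/63% at r = 0.3/0.5/0.7 and shortens the 95% interval by about 5/13/29%. The benefit ranges from slight to substantial with a correlation the documents do not give.

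A non-significant baseline test does not show equality: at 30 per arm it is compatible with a gap of 0.52 SD, and a gap above 0.25 SD arises in about one randomisation in three for any one outcome. The resulting shifts are expected values given the gap, not minimum or certain ones. Since the data are already collected, the improvement is nearly free and should be made.

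**What to change.** In section 2.12, replace the post-intervention t test with ANCOVA: the two-week value regressed on treatment group and the baseline value of the same outcome, reporting the adjusted difference with its 95% interval. Apply it whatever the baseline table shows. For the Oxford grade, where a mean difference is hard to interpret, consider a proportional-odds model on group adjusted for baseline grade, after checking that it can be fitted at this sample size.

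Replace Hypothesis 1 and the baseline t tests with descriptive summaries by group. If section 2.12 meant change scores, say so, and still use ANCOVA.

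The cost is protocol wording and one regression per outcome: 11 ANCOVAs and one ordinal model. No participants, visits or measurements are added. Section 2.13 has the study ending in July 2024, so timing matters: make the change before unblinded results are examined, or report it as a deviation alongside the planned t test.

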3. EXPECTED OUTCOME

The main outcome of this research study find the effectiveness of Thoracic mobility exercise in comparison with manual release technique in treating upper back pain. Over all expected outcome of the research is thoracic mobility exercise will be more effective than manual release technique which includes myofascial release and Maitland's thoracic mobilization technique. Thoracic mobility exercises involve a series of movements and stretches aimed at improving the flexibility, range of motion, and strength of the thoracic spine and spinal extensors. These exercises can target specific muscle groups and promote better posture and spinal alignment. It is anticipated that thoracic mobility exercises will help patients by addressing the root causes of upper back pain. These exercises may improve posture, reduce muscle imbalances, and increase the overall mobility of the thoracic spine.

Myofascial release involves applying sustained pressure to specific trigger points or knots in the muscles and fascia of the upper back. Maitland's thoracic mobilization technique, on the other hand, is a hands-on manual therapy approach that focuses on joint mobilization and spinal manipulation. It provide immediate pain relief by targeting specific areas of tension or dysfunction in the upper back.

In this research, Pain intensity is measured using VAS Scale; Both intervention targeting pain relief; therefore it provides significant pain relief after the administration. In terms of Range of Motion, Strength and Disability, thoracic mobility exercise will provide more improvement compared to the manual therapy technique. Thoracic mobility exercise will provide long term benefit when compared to the manual therapy technique by eliminating root cause of upper back pain.

4. REFERENCES:

Akulwar-Tajane, I. *et al.* (2021) 'Effects of COVID-19 pandemic lock down on posture in physiotherapy students: A cross-sectional study', *Medical & Clinical Research*, 6(1), pp. 91–102.

Amro, A. *et al.* (2020) 'Musculoskeletal disorders and association with social media use among university students at the quarantine time of COVID-19 outbreak'.

5. APPENDICES

5.2 Annex: II: Data Collection tool

5.2.1 Pre Test Questionnaire

Effectiveness of Thoracic mobility exercises versus manual release technique in minimizing mechanical upper back pain among undergraduates in Sri Lanka

1. Personal Details

1.1 Name :

1.2 Address:

1.3 Permanent Address:

1.4 Phone / Mobile No:

Code No:.....

Effectiveness of Thoracic mobility exercises versus manual release technique in minimizing mechanical upper back pain among undergraduates in Sri Lanka

Code No:.....

2. Demographic Data

2.1 Age :

2.2 Gender :

2.3 Height :

2.4 Weight :

2.5 BMI :

2.6 Family Size :

2.7 Bread Winner of the family:.....

2.8 Monthly Income :

2.9 Financial support for study:.....

Pre Test Questionnaire

3. Pain related questions:- Baseline

3.1 How long have you been experiencing Upper back or thoracic pain?

.....

3.2 When did your pain occur for the first time?

[figure not shown]
.....

3.3 What are the treatments that you underwent so far?

.....

In the following scale, mark a number which best describes your pain. Number “0” indicates “no pain at all”, and number 10 indicates “the worst pain ever possible”. You

have to denote the number which best describes your pain in following instance and please denote the number respective to each activity in the following chart.

Aspect	VAS/ Pain scale number
3.4 Present Pain Intensity	
3.5 Sitting	
3.6 forward Bending	
3.7 Standing	
3.8 Walking	
3.9 Sleeping	
3.10 Transferring	
3.11 Performing day to day activities	

4. Range of Motion (ROM) – Base Line

Joint	Movement	ROM
Thoraco- Lumbar	Flexion	
	extension	

5. Muscle Strength – Base Line

Muscle strength of Thoracic spine extension	MMT Scale (Oxford- Grading Scale)

6. Pain- Self- efficacy Questionnaire (PSEQ) – Baseline

Please rate how confident you are that you can do the following things at present, despite the pain. To indicate your answer tap one of the options on the scale under each item, from "not at all confident" to "completely confident".

(Fill the appropriate field only)

	0 "not at all confident"	1	2	3	4	5	6 "completely confident"
I can enjoy things, despite the pain.							
I can do most of the household chores (e.g. tidying-up, washing dishes, etc.), despite the pain.							
I can socialise with my friends or family members as often as I used to do, despite the pain.							
I can cope with my pain in most situations.							
I can do some form of work, despite the pain. ('work' includes housework, paid and unpaid work).							
I can still do many of the things I enjoy doing, such							

as hobbies or leisure activity, despite pain.						
I can cope with my pain without medication.						
I can still accomplish most of my goals in life, despite the pain.						
I can live a normal lifestyle, despite the pain.						
I can gradually become more active, despite the pain.						

5.2.2 Post Test Questionnaire

[figure not shown]
Effectiveness of Thoracic mobility exercises versus manual release technique in minimizing mechanical upper back pain among undergraduates in Sri Lanka

Post Test Questionnaire

Code No:.....

1. Pain related questions:

In the following scale, mark a number which best describes your pain. Number “0” indicates “no pain at all”, and number 10 indicates “the worst pain ever possible”. You have to denote the number which best describes your pain in following instance and please denote the number respective to each activity in the following chart

Aspect	VAS/ Pain scale number
1.1Present Pain Intensity	
1.2Sitting	
1.3forward Bending	
1.4Standing	
1.5Walking	
1.6Sleeping	
1.7Transferring	
1.8Performing day to day activities	

2. Range of Motion (ROM)

Joint	Movement	ROM
Thoraco- Lumbar	Flexion	
	extension	

5. Muscle Strength

Muscle strength of Thoracic spine extension	MMT Scale (Oxford- Grading Scale)

6. Pain- Self- efficacy Questionnaire (PSEQ)

Please rate how confident you are that you can do the following things at present, despite the pain. To indicate your answer tap one of the options on the scale under each item, from "not at all confident" to "completely confident".

(Fill the appropriate field only)

	0 "not at all confident"	1	2	3	4	5	6 "completely confident"
I can enjoy things, despite the pain.							
I can do most of the household chores (e.g.							

tidying-up, washing dishes, etc.), despite the pain.						
I can socialise with my friends or family members as often as I used to do, despite the pain.						
I can cope with my pain in most situations.						
I can do some form of work, despite the pain. ('work' includes housework, paid and unpaid work).						
I can still do many of the things I enjoy doing, such as hobbies or leisure activity, despite pain.						
I can cope with my pain without medication.						
I can still accomplish most of my goals in life, despite the pain.						
I can live a normal lifestyle, despite the pain.						
I can gradually become more active, despite the pain.						

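### The self-rating forms carry the full study title naming both treatments, an avoidable expectation cue in a trial that describes its participants as blinded

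*Combined protocol and SAP*

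**What the plan says.** **Form headings.** In the combined protocol and SAP, the post-test questionnaire (5.2.2) is headed "Effectiveness of Thoracic mobility exercises versus manual release technique in minimizing mechanical upper back pain among undergraduates in Sri Lanka". The pre-test questionnaire (5.2.1) prints the same title twice, above the personal details and again above the demographic items. No neutral form title is described, and nothing says that the heading is withheld from participants.

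**Who does the rating.** Section 2.9 makes pain a self-report: "Subjects will be asked to mark the number between 0 and 10 that fits best to their pain intensity". Below the title, the post-test form addresses the participant directly: "In the following scale, mark a number which best describes your pain". The self-efficacy items (PSEQ) follow in the same form: "Please rate how confident you are that you can do the following things at present, despite the pain".

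**Blinding and arms.** Section 2.4 states "Participants and assessors will be blinded". It then sets out an "experimental group which will receive thoracic mobility exercises and control group which will receive myofascial release and joint mobilization treatment".

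**Expectation.** Section 3 states the investigators' view: "Over all expected outcome of the research is thoracic mobility exercise will be more effective than manual release technique".

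**The concern.** Pain intensity is the outcome named in the study title and general objective, and it is scored by the participant. A participant knows which treatment he or she is having. Knowledge of the comparator, and a hint about which treatment is being tested, can turn that into different ratings in the two arms even when the treatments work equally well. Range of motion and muscle strength are recorded by an assessor and are less exposed.

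A heading that names both treatments puts this information in front of the participant at the time of rating. A blinded-participant claim would normally lead a reader to assume that such cues had been removed. If they have not, a between-arm difference in self-ratings is harder to attribute to treatment, and the blinding label overstates the protection.

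**Working it through.** The documents give no figure for an expectation effect, so no calculation can size it. The check sets the relevant places side by side.

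1. **What the heading discloses.** It names two treatments, exercise first and manual release after *versus*. It therefore tells every participant what the other arm receives. It does not use the words experimental, control or new, and it does not state an expected result.

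2. **What is rated beneath it.** The post-test form has 8 pain items and 10 PSEQ items, so 8 + 10 = 18 self-rated entries. It also has 2 range-of-motion fields and 1 strength field, so 2 + 1 = 3 assessor-recorded entries. Of the 18 + 3 = 21 entries, 18 come from the participant.

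3. **What participants already know.** Section 5.3 has one group performing three exercises twice a day. The other lies prone while a therapist applies sustained pressure and oscillating mobilization. Nobody could confuse the two. The participant half of the blinding statement in 2.4 therefore cannot mean blinding to the treatment received. At most it could mean not knowing the comparator or the hypothesis. The heading removes the first and may weaken the second.

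4. **Which form matters for the analysis.** Section 2.12 compares the groups after the intervention with a two-sample t test and describes no baseline adjustment. Baseline ratings do not enter that comparison, so the post-test form is the one that counts. On the pre-test form the title appears on the opening sheets and is not repeated where the pain items begin, so the cue there is weaker.

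5. **Whether assessors are affected.** The range-of-motion and strength fields sit under the same heading. The title shows both treatments but not the individual's allocation, so it does not by itself unblind an assessor.

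6. **What cannot be seen.** Section 2.10 requires written informed consent. The consent pages were not available for this review. If they name both treatments, the form heading only repeats something already disclosed.

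**The case against.** The strongest reply is that the heading may add nothing. Participants know their own treatment, consent may already have named the alternative, and a neutral title would not make them blind. This stands as a limit on the size of the point. It does not remove it: a reminder printed on the rating form differs from disclosure at enrolment, and leaving it off costs almost nothing.

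Three stronger readings are tempting, and the documents do not support them.

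- **A reader might infer that the forms reveal the expected winner.** They do not. The title sets two active treatments against each other. The investigators' expectation is in section 3, and nothing shows that participants see that section. The hypotheses in section 2.5 are two-sided.
- **A reader might infer that any bias must favour exercise, as the plan expects.** The overall statement in section 3 does favour exercise. For pain, however, the same section predicts relief from both treatments and credits manual treatment with immediate relief. The specific advantages it claims for exercise are in range of motion, strength and disability. It makes no prediction for self-efficacy by name. The direction of a shift in self-ratings is therefore open.
- **A reader might try to express the harm as an inflated false-positive rate.** That requires an assumed shift in ratings for which the documents give no basis. It would also charge the heading with the whole effect of participants knowing their treatment, most of which would remain under any heading.

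**Conclusion.** The point holds in a limited form. The plan calls participants blinded, yet the post-test form, and the opening sheets of the pre-test form, show them both treatments by name. On the post-test form this stands above the items on which they rate their own pain and self-efficacy. It is an avoidable cue for expectation bias.

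The size and direction of any bias cannot be determined from the documents. The conclusion rests on two assumptions: that participants complete the forms as laid out in the appendix, heading included, and that the consent material does not already disclose as much. If the second fails, the heading adds little.

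The blinding statement needs correcting whatever the heading says, because the two treatments are plainly distinguishable. This is a minor improvement and does not threaten the design.

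**What to change.** **Forms.** Replace the title on both questionnaires with a heading that names no treatment, for example *Upper back pain study - questionnaire*, plus the code number. Do the same for any other sheet the participant handles while rating. Make the change before forms are issued, because the cue cannot be removed from ratings already collected.

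**Section 2.4.** Stop claiming that participants are blinded to treatment and describe the trial as assessor-blinded. Make clear that this protects the assessor-recorded measures and not the self-rated ones. Add that participants are unaware of the study hypothesis only if the consent and information material bears this out; otherwise one unsupported statement would replace another.

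**Cost.** Two forms to edit and reprint, and a less favourable blinding label. Sample size, treatments and analysis are unchanged.
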